### SCREENING PHASE/ INCLUSION CRITERIA

Men with PCa, diagnosed by **MRI prostate** and **MRI/Ultrasound (MRI/US) fusion prostate biopsy with KOELIS Trinity®**, who have selected radical prostatectomy (RP) as their treatment (n=15).

First 5 participants undergo microwave ablation and immediate prostatectomy.  
Following 10 participants undergo microwave ablation and 1 month delayed resection

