## **7.0 ADVERSE EVENTS**

### **7.1 Experimental Therapy**

#### **7.1.1 One-month delayed resection**

Prostate cancer is usually a slow-growing cancer even in the setting of high-risk disease. Therefore, delaying RP doesn't impact on earlier, medium- or long-term oncologic and functional outcomes [44-46]. On a period of one month from TMA to RALP, the functional outcomes should not be affected by the TMA. In fact, the one-month delay from TMA to RP is long enough to allow for decreasing peri-prostatic edema, however short enough to avoid tissue fibrosis, retraction and adhesion that would happen with prolonged delay from TMA. The functional outcomes should be dictated/related to RALP, patients' and cancer characteristics such as nerve sparing RALP technic, urethral length, patients age, etc. The TMA will not be performed with a curative intent, in fact, it will be performed conservatively, sparing the boundaries of the prostate to avoid damage to the neurovascular bundles and the rectum. Furthermore, there will be a dose-escalation approach, where the TMA will be performed from small to larger ablation areas allowing for precise evaluation of the ablated area in each planned ablation template.

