## **7.7 Monitoring Rules for Safety**

All other adverse events- such as those that are expected or are unlikely or definitely not related to the study participation- are to be reported as part of regular data submission.

---

We will pause study enrollment after 10 patients if 2 or more patients do not progress to RP and perform a thorough assessment as to ongoing safety of the study.

If a severe adverse event related to TMA occurs during TMA procedure or by follow-up phase (Day 10 ± 5) for immediate resection phase or by follow-up phase 3 (Day 40 ± 5) for delayed resection phase, we assess, discuss, and tabulate the severe adverse event.

To ensure safety, the next patient's TMA will be scheduled at least after follow-up phase of the previous patient for immediate resection phase. For delayed resection phase, the next patients for the different TMA template will be scheduled at least after follow-up phase 3 of the previous patients.

In addition, for the delayed resection phase, in the case that two in two patient who underwent the same TMA template experienced severe adverse events related to TMA, we stop to proceed the next TMA template.

We set 30% as clinically acceptable severe adverse events (defined as CDC ≥3) rate (i.e. less than 4 in 10 delayed resection cases).

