#### **10.6 Sample Size and Patient Accrual**

Due to the nature of exploratory and feasibility study design, the sample size of 15 subjects was determined by practical considerations, including cost and feasibility (could not do many more during the funding period).

Through the immediate resection phase, 5 practical TMA templates and their ablation areas are evaluated. With following the delayed resection phase, the short-term safety and feasibility of TMA templates are evaluated.

The number of patients included may be extended considering the need to evaluate different treatment parameters (still according to manufacturer data).

---

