## 10.7 Data Analyses Plans

All patients who sign the consent form will be registered and entered the database. For each patient, we will list whether he received the assigned protocol (and if not, the reasons), the outcome of the procedures, compliance with the protocol (and reasons for failure to comply), adverse events with any of the procedures, MRI results, and targeted biopsy results.

- The data from the immediate resection phase and delayed resection phase will be separately evaluated. The observed ablated area in immediate resected prostatectomy specimen based on TTC staining will be compared with the predicted ablation area according to the template. The tissue viability will be evaluated by HE staining on delayed resection prostatectomy specimen.
- The comparison of the difference between the treatment effect dimensions measured histologically on the prostatectomy specimen resected after TMA and the predictive ablation charts provided by the manufacturer will be performed. For this analysis, the data from immediate resection phase and delayed resection phase are separately evaluated.
- The comparison between the treatment effect dimensions measured histologically on the prostatectomy specimen resected one month after TMA, compared to post TMA dimensions measured on the pre-RP mpMRI.
- To evaluate the intra/post-operative safety of TMA, we defined 30% as clinically acceptable severe adverse events (defined as CDC  $\geq 3$ ) rate. If the severe adverse events occur less than 30% (equivalent to less than 4 cases in 10 cases) for the delayed ablation phase, the feasibility of TMA is proved.

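### The delayed-phase pass criterion pools severe events over five templates, so feasibility can be declared even if both men on Template 5, the last, have a severe event

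*Combined protocol and SAP*

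**What the plan says.** Section 10.7 fixes an acceptable rate: "we defined 30% as clinically acceptable severe adverse events (defined as CDC" grade 3 or higher) . The pass rule follows: "If the severe adverse events occur less than 30% (equivalent to less than 4 cases in 10 cases) for the delayed ablation phase", and the consequence is that "for the delayed ablation phase, the feasibility of TMA is proved". Section 7.7 repeats the count as "less than 4 in 10 delayed resection cases". Neither place names a template.

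The denominator comes from the study schema: "Following 10 participants undergo microwave ablation and 1 month delayed resection". Section 4.2 places these men two at a time on Templates 1 to 5 (patients 6-7, 8-9, 10-11, 12-13 and 14-15). Section 7.1.1 describes the plan this way: "there will be a dose-escalation approach, where the TMA will be performed from small to larger ablation areas". Section 10.6 says of the delayed phase that "the short-term safety and feasibility of TMA templates are evaluated", in the plural.

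There is one template-level rule, in 7.7 and again in 10.7. If both men on the same template have severe events related to TMA, then "we stop to proceed the next TMA template".

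**The concern.** The stated target of the delayed phase is the templates, but the decision is taken on an average over them. Events confined to one template are diluted by the eight men treated on the others. The template-level rule does not repair this. It acts on progression, and Template 5 has no successor. Even on Templates 1 to 4 it is not connected to the feasibility sentence.

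So the plan, followed as written, could state feasibility without qualification when the last and longest configuration had severe events in both men. The study summary plans an analysis to determine the delivery protocol, and 10.1 looks ahead to TMA as a stand-alone treatment. An unqualified statement could therefore be carried over to a configuration for which the data point the other way.

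**Working it through.** **Inputs from the documents.** Ten delayed-phase men, two on each of five templates (study schema, 4.2). Pass if below 30%, glossed as fewer than 4 of 10 (7.7, 10.7). Progression stops at 2/2 on a template (7.7, 10.7). No template-specific event rate is given.

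**1. The plan's own threshold.** 3/10 = 30%, which is not less than 30%. The percentage wording therefore allows at most 2 cases, while the count wording allows at most 3. The count matches the percentage only if the rule is read as at most 30%. The two wordings disagree at exactly 3 cases, so both are carried below.

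**2. The pattern at issue, which needs no assumed rates.**
- Templates 1 to 5 with 0, 0, 0, 0, 2 events: 2/10 = 20%, Clopper-Pearson 95% CI 2.5% to 55.6%. It passes under both wordings.
- One further event: 3/10 = 30%, CI 6.7% to 65.2%. It passes only under fewer than 4.
- Template 5 alone: 2/2, CI 15.8% to 100%.

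**3. How many patterns pass.** To reach Template 5, each of Templates 1 to 4 must have 0 or 1 event, which gives 2^4 = 16 patterns. With 2/2 on Template 5, fewer than 4 in total allows at most one earlier event: 1 + 4 = 5 of 16 patterns. At most 2 in total allows none: 1 of 16. The patterns are not equally likely.

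**4. Probabilities under assumed rates.** Let p1 to p5 be the severe-event rates per man, with men independent and one event definition for both rules. Let q0 = Π(1−pi)² and S = Σ 2pi/(1−pi), both over Templates 1 to 4.
- P(pass and 2/2 on Template 5), fewer than 4 events: p5² · q0 · (1 + S)
- The same with at most 2 events: p5² · q0
- P(no earlier 2/2): Π(1 − pi²) over Templates 1 to 4
- P(pass given 2/2 on Template 5 and no earlier stop): q0(1 + S) or q0, divided by Π(1 − pi²)

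Worked case with rates 5, 5, 10, 20 and 30%: q0 = 0.95² × 0.95² × 0.90² × 0.80² = 0.4222, and S = 0.1053 + 0.1053 + 0.2222 + 0.5000 = 0.9327. The joint chance is 0.09 × 0.4222 × 1.9327 = 0.073 (fewer than 4) or 0.09 × 0.4222 = 0.038 (at most 2). Π(1 − pi²) = 0.9457, so the conditional chances are 0.8161/0.9457 = 0.86 and 0.4222/0.9457 = 0.45.

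| Assumed rates, Templates 1-5 (%) | Joint, <4 | Joint, ≤2 | Conditional, <4 | Conditional, ≤2 |
|---|---|---|---|---|
| 13, 13, 13, 13, 13 | 1.2% | 0.6% | 77% | 35% |
| 5, 5, 5, 10, 20 | 3.7% | 2.4% | 93% | 61% |
| 5, 5, 10, 20, 30 | 7.3% | 3.8% | 86% | 45% |
| 2, 5, 10, 30, 60 | 28% | 12% | 85% | 38% |
| 5, 5, 10, 30, 70 | 36% | 16% | 83% | 36% |
| 0, 0, 10, 40, 80 | 48% | 19% | 90% | 35% |

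The 13% row borrows the figure that 7.1.2 gives for adverse events after HIFU. It is not a TMA rate and not a rate of grade 3 or higher events. All six rows are assumptions.

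**5. A related gap at Template 4.** If both men there have severe events and no one earlier does, progression stops at 8 men with 2/8 = 25%. The documents do not say whether feasibility is then declared.

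**The case against.** The strongest reply is that this is a 10-man exploratory cohort sized by practicality (10.6), for which pooling is an ordinary choice. Two men carry almost no information about a template: even 0/2 has a one-sided 95% upper bound of 1 − √0.05 = 77.6%. That stands, and it rules out a pass or fail test per template. It does not support an unqualified statement of proof.

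It can also be said that the information will be visible anyway. Section 10.7 lists adverse events for each patient and requires severe events to be tabulated, templates follow patient number, and the DSMC reviews safety. That is true, but no by-template display is required and none of it enters the conclusion rule.

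Several stronger readings are tempting and are not supported:
- *A pass clears every template, or recommends Template 5.* Nothing says so. Section 1.3 assigns the optimal protocol to the first five cases and practical feasibility to the next ten, and the 10.7 sentence is about TMA overall.
- *The 2-of-2 rule marks a template as unacceptable.* It is a progression rule. It counts TMA-related severe events, a restriction that the pass sentence does not state.
- *A misleading pass is likely.* The 28% to 48% figures need a 60% to 80% severe-event rate on Template 5. No document supports such rates, and 7.1.2 expects fewer side effects than after curative-intent HIFU.
- *The templates are five rising sizes.* They are five configurations of three ablation times. Planned total times are 2 × 3 = 6, 2 × 5 = 10, 7.5, 2 × 5 = 10 and 2 × 7.5 = 15 minutes, which do not rise at every step, and 4.2 lets the physician modify delivery.

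**Conclusion.** The point holds as a defect in the conclusion rule. Two of two on Template 5 with no other event passes under either wording, and no provision qualifies the resulting statement. This rests only on the planned layout of two men per template, which extension of enrolment or modified delivery could change.

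How often it would happen cannot be derived from the documents. The joint chance ranges from about 1% to 48% under the count wording and from 0.6% to 19% under the percentage wording, driven mainly by the rate assumed for Template 5. The conditional figure depends less on that assumption: once both Template 5 men have had a severe event without an earlier stop, the trial still passes in 77% to 93% of runs (fewer than 4) or 35% to 61% (at most 2) across the six vectors. The criterion is therefore a weak detector of events concentrated on the last template. This is a cheap improvement to reporting and wording, not a flaw in the design.

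**What to change.** In 10.7:
- Report severe events as x/2 for each template beside the pooled x/10 with its exact 95% CI, using the numbers actually treated.
- State one event definition, TMA-related or all severe events, and use it for both the template counts and the pooled criterion.
- Replace the claim of proof with a statement limited to the average over the templates actually given.
- State that any template meeting the plan's own 2-of-2 condition, including Template 5, is reported separately and is not covered by the feasibility statement. This also settles what is said if the study stops at Template 4.
- Reconcile the percentage and count wordings, here and in 7.7. Which one applies is for the investigators.

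The cost is a few sentences and one small table, with no added patients or data. The downside is a narrower feasibility claim. No change to the templates, the stopping rule or the acceptable rate is proposed.

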### Immediate resection phase

If a severe adverse event related to TMA occurs during TMA procedure or by follow-up phase (Day  $10 \pm 5$ ), we assess, discuss, and tabulate the severe adverse event. For this evaluation, TMA-related adverse events include rectal injury, and urethral injury.

### Delayed resection phase

If a severe adverse event related to TMA occurs during TMA procedure or by follow-up phase 3 (Day  $40 \pm 5$ ), we assess, discuss, and tabulate the severe adverse event. In the case that two in two patient who underwent the same TMA template experienced severe adverse events related to TMA, we stop to proceed the next TMA template. For this evaluation, TMA-related adverse events include rectal injury, urethral injury, acute urinary retention, and uncontrollable hematuria.

Adverse events are also recorded in accordance with Common Terminology Criteria for Adverse Events (CTCAE) v5.0.

- TMA procedure duration: probe-in / probe-out time, ablation time will be recorded.
- The ablation location in the prostate as seen in the KOELIS 3D map and the ablation location observed histologically on the prostatectomy specimen will be recorded.

---

- The change in functional outcomes between baseline and each follow-up visit, using IPSS, IIEF-5, EPIC-26 and uroflowmetry is recorded. For delayed resection phase, functional outcomes between baseline and follow-up phase 2 will be estimated as average change.
- The post-TMA MRI and prostate biopsy performed just prior to the delayed radical prostatectomy will be reported.

## 10.8 Reporting and Exclusions

- Evaluation of toxicity.

We will monitor for TMA related toxicities such as rectal injury, urethral injury, acute urinary retention, perineal pain and uncontrollable hematuria. Complications will be managed as per standard of care in accordance with CDC.

- Evaluation of response. NA.

## 11.0 STUDY MANAGEMENT

### 11.1 Conflict of Interest

All investigators will follow the University conflict of interest policy. Any USC investigator who has a conflict of interest with this study (patent ownership, royalties, or financial gain greater than the minimum allowable by their institution, etc.) must complete a "Statement of Outside Interests Related to Research" Form. The application is reviewed and approved by the Conflict of Interest Review Committee (CIRC) USC conflict of interest policy is available at <http://ooc.usc.edu/conflict-interest-research>

### 11.2 Institutional Review Board (IRB) Approval and Consent Process

It is expected that the IRB will have the proper representation and function in accordance with federally mandated regulations. The IRB should approve the consent form and protocol and all study related documents used in the study (e.g. QOL questionnaire, pill diary, brochure, advertisement etc).

In obtaining and documenting informed consent, the investigator should comply with the applicable regulatory requirement(s), and should adhere to Good Clinical Practice (GCP) and to ethical principles that have their origin in the Declaration of Helsinki.

Before recruitment and enrollment onto this study, the patient will be given a full explanation of the study and will be given the opportunity to review the consent form. Each consent form must include all the relevant elements currently required by the FDA Regulations and local or state regulations. Once this essential information has been provided to the patient and the investigator is assured that the patient understands the implications of participating in the study, the patient will be asked to give consent to participate in the study by signing a dated IRB-approved consent form.

---

Prior to a patient's participation in the trial, the written informed consent form should be signed and personally dated by the patient and by the person authorized to obtain the informed consent

**11.3 Required Documentation (for multi-site studies)**

Not required

**11.4 Registration Procedures**

**USC Registration:**

The Research Coordinator must complete the protocol eligibility form to ensure that the patient is eligible. The PI will review the patient eligibility (with assistance from the Research Coordinator- who will assemble the required source documents, and do an initial review) prior to registering the patient on study.

The Research Coordinator or data manager will then register the patient into the Cancer Center database, Café, by accessing the Registration forms. Likewise, after the patient has completed the study, the Off Study forms in cafe will need to be completed, for Off Treatment and Off Study.

**11.6 RECORDS AND DATA SUBMISSION**

**A. Confidentiality of Records**

The original data collection forms will be kept in secure file cabinets, for USC patients forms will be kept in the Clinical Investigations Support Office (CISO).

**B. Patient Consent Form**

At the time of registration, signed and dated copies of the patient Informed Consent with the Human Rights and the HIPAA authorization must be given to the patient. Institutional policy regarding distribution and location of original consent documents should be followed. When a study is opened at two or more institutions, a copy of the signed consent and HIPAA should be sent to USC CISO QA team as soon as possible, and not later than within 5 business days of obtaining consent. For patients consented at USC/LAC, institutional policy should be followed: a copy of ICF and HIPAA should be uploaded through True to USC CRO and to CISO QA Team. The original will be kept in the patient research chart maintained by the study assigned Data Manager.

**C. Registration Eligibility Worksheet**

At the time of registration, the completed Eligibility Worksheet will be submitted to the QA Monitor at CISO for review of eligibility compliance.

**D. Data Collection Forms and Submission Schedule**

If a treatment trial, protocol data will be entered into eCRFs in Café.

Within two weeks of registration, the data manager will complete the initial set of On Study forms and baseline Toxicities

Within two weeks of completion of each course of treatment, the data manager must complete the Course Assessment, Toxicities, and if appropriate Response data.

---

- After Off Treatment, within two weeks of each follow up, complete the Follow Up forms.

## 11.7 Data Management and Monitoring/Auditing

### 11.7.1 Active Monitoring Program Details

- a. **Adherence to Protocol/Per Patient:** It is the responsibility of the Principal Investigator (PI) to ensure that patient recruitment and enrollment, treatment, follow-up for toxicities and response, and documentation and reporting are all performed as specified in the protocol.
- b. **Day-to-Day Monitoring – Eligibility:** The Study Coordinator will assist the investigator in reviewing eligibility and will assemble the required source documents, and do a final review by completing an Eligibility Registration Worksheet. The Eligibility Registration Worksheet with a copy of Informed Consent and supporting source documents will be submitted to CISO QA via email or Fax for verification prior to registering the patient on study.
- c. **Day-to-Day Monitoring – Informed Consent:** Prior to registering the patient on study, the Study Coordinator will review the informed consent, to ensure that the patient has signed and dated the most current IRB-approved form, and that the form has been signed and dated by the person obtaining the consent as well as appropriate witnesses. A copy of the ICF will also be provided to CISO QA for review. CISO SOP 3.3 will be followed.
- d. **Day-to-Day Monitoring – Treatment:** The PI and co-investigators are responsible for ensuring that treatment is given per protocol. The Study Coordinator will review the treatment orders with the treating investigator. The treating investigator will review the status of each patient on-study, with the Study Coordinator and the treating physician, on an on-going basis.
- e. **Data Management – Patient Charts:** At USC, all written source documents not associated with the study research are maintained in the patient chart, which is stored in the Department of Medical Records at the appropriate hospital. At the Norris Hospital, the official medical record is the Electronic Patient File (EPF). Radiographical images are stored in the Department of Radiology and in an electronic system called Synapse. These are the permanent, official documents for each patient on-study. A copy of the signed informed consent, physician's notes, orders, test results and pathology notes are maintained in the patients' hospital charts. It is the responsibility of the research staff to ensure that the patient chart contains the required documents and work closely with treating investigators to ensure all protocol-related assessments are carefully documented.
- f. **Data Management – Research Charts:** To facilitate adherence to the protocol schedule and data management, research charts are created to collect copies of the relevant notes, orders and results, that are in the Patient Chart. In Addition, all source documents related to the research, such as original informed consent forms, HIPAA Forms, AE assessment worksheets, disease response worksheets and NTFs are maintained in the Research Charts. Protocol calendars, worksheets, and checklists, are also kept in the research chart. These are maintained in the Clinical Investigation Support Office until the study is completed and the results are published and no further need is anticipated.

---

These are then stored off-site. It is the responsibility of the Data Manager to ensure that the research chart contains all the required documents.

g. **Data Management – Case Report Forms:** It is the responsibility of the Data Manager to complete the required case report forms. The case report forms are developed for the trial and these are used to finalize the data entry screens in the Cancer Center clinical trials database. It is the responsibility of the PI to review the Off-Study Summary form which summarizes pertinent toxicity, response and adherence information, once the patient has completed treatment.

